**Comparative Effectiveness of Particulate Versus
Nonparticulate Corticosteroid Injections for the Treatment
of Musculoskeletal Conditions**

Study Protocol and Statistical Analysis Plan

NCT04278833

April 7, 2020

1) Name of study:

Comparative Effectiveness of Particulate versus Nonparticulate Steroid Injections for Treating Musculoskeletal Conditions

2) PI and other key investigators or key study personnel

PI: [name]

Investigator: [name]

Research coordinator: [name], CCRC

3) Specific source of institutional funding (account number): None**4) List of sources from whom you are seeking funds (or have sought funding) for this project**

AMSSM funding

Stanford internal funding

PM&R foundation

Charity from donors

5) Specific aims and basic hypothesis including an explicit primary hypothesis or goal**Specific Aims:**

- a. To determine if particulate or non-particulate corticosteroid injections are more effective at treating pain from musculoskeletal pathologies of the intra-articular hip, glenohumeral joint, biceps tendon, and subacromial bursa at 2 weeks, 3 months, or 6 months.
- b. To determine if there is a significantly different side effect profile between particulate and non-particulate corticosteroids when used for intra-articular hip, glenohumeral joint, biceps tendon, or subacromial bursa injections.

Hypothesis: There will be no significant difference in pain reduction, number of injections received, conversion to surgery, or side effect profile at 2 weeks, 3 months, or 6 months between particulate and non-particulate corticosteroids in the treatment of musculoskeletal pathologies of the intra-articular hip, glenohumeral joint, biceps tendon, or subacromial bursa.

6) General background

Corticosteroid injections are commonly used for the treatment of painful musculoskeletal pathologies including hip and glenohumeral joint osteoarthritis, adhesive capsulitis, biceps tendinopathy, and impingement syndrome/subacromial bursitis (Lambert et al, 2007; Lee et al, 1997; Yoon et al, 2013; Hong et al, 2011), yet there is no consensus on whether particulate or non-particulate steroids are superior. Particulate steroids include betamethasone, triamcinolone, and methylprednisolone, while non-particulate steroids include dexamethasone (Derby et al, 2008).

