While particulate steroids might have theoretical improved efficacy due to possible decreased dispersion from the intra-articular space, there is animal data to suggest that particulate steroids may decrease microvascular perfusion (Laemell et al, 2016). Moreover, during animal studies in which steroids were directly injected into the arterial circulation, particulate but not non-particulate steroids resulted in permanent central nervous system damage (Dawdley et al, 2009; Okubadejo et al, 2008). Yet because there is no meaningful data to support one choice over another, there remains significant clinical equipoise.

This is in contrast to spinal epidural corticosteroid injections, where dexamethasone is generally preferred due to comparable efficacy and improved safety profile of non-particulate steroids compared to particulate steroids (Kennedy et al, 2014; Mehta et al, 2017).

While randomized controlled trials have been completed comparing particulate to non-particulate steroids in the treatment of spinal stenosis (Kennedy et al, 2014; Mehta et al, 2017), knee rheumatoid arthritis (Hajialilo et al, 2016), and idiopathic trigger finger (Ring et al, 2008) with conflicting results, there have been no studies comparing these two steroid types in the hip joint, glenohumeral joint, biceps tendon, or subacromial/subdeltoid bursa.

7) Preliminary unpublished data: None

8) Experimental design and data analysis, including inclusion and exclusion criteria, statistical basis for the number of subjects to be enrolled, the statistical plan for analyzing at least the primary hypothesis, matrix showing procedure plan for each study visit, data safety monitoring plan .

Design

This will be a single center, prospective, single blind, randomized controlled trial of hip, glenohumeral joint, peri-tendinous biceps brachii, and subacromial bursa injections comparing the efficacy of particulate (triamcinolone, betamethasone) versus non-particulate (dexamethasone) corticosteroids.

Participants will be recruited for the study by trained physicians and physician extenders at Stanford orthopedic and PM&R clinics only after they have already opted for corticosteroid injection as a part of their routine medical care. The initial decision to pursue steroid injection will be based entirely on joint decision making between the patient and their medical provider prior to mention of the study.

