After consenting, basic demographic data, average numeric pain score (NRS) over the past week, and information on other medical interventions tried for their pain (including medication use, physical therapy, chiropractic care, and massage) will be collected. The participant will then be randomized to receive either a particulate (triamcinolone or betamethasone) or non-particulate (dexamethasone) corticosteroid, both of which are within current standards of care. Ultrasound or fluoroscopic guided injection will then be completed using sterile technique as per current clinic practice.

After the injection, patients will follow up in clinic or over the phone at 2 weeks, 3 months, and 6 months and will be asked their average NRS over the past week, functional questionnaires appropriate to pertinent body parts (WOMAC, ASES, QDASH), other treatments they have tried in the interim, and for any side effects they have experienced. In addition to obtaining outcome measures, the treating physicians may order repeat injections, medications, or refer the subject to surgery, at their discretion based upon the patient's pain and functional limitations. Up to a total of three injections to the same musculoskeletal structure are allowed during the 6 month study period. Any injection into a separate space (i.e. glenohumeral joint followed by subdeltoid bursa) will be considered different structures, and follow up for the new anatomical site will begin at the time of that injection. Data collection and follow up on the previous anatomical injection site will continue on the same timeline. Data on number and timing of repeat injections, surgeries, side effects, and medications will be recorded as part of the study.

Data analysis

Patients receiving injections to the intra-articular hip, glenohumeral joint, peri-tendinous biceps, and subdeltoid bursa will be analyzed separately. Depending on normality and cell counts, baseline measures between the particulate and non-particulate injection groups will be compared using two-sample t-tests or Mann-Whitney U-tests for continuous variables and chi-squared tests or Fisher's exact tests for categorical variables.

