Within each joint/structure, a mixed-effects model will be used to compare differences in pain (NRS), function (WOMAC, ASES, QDASH), and the number of subsequent injections. These models will include adjustments for repeated measures and potential covariates as determined by the previous univariate tests. A power analysis determined that a sample size of 50 (25/group) will provide at least 80% power to detect 10% differences in pain and 25% differences in function between patients receiving particulate and non-particulate corticosteroids in the subdeltoid bursa and intra-articular hip, while a sample size of 36 (18/group) achieves the same power for patients receiving treatment in the glenohumeral joint, and a sample size of 62 (31/group) achieves this power in the biceps brachii group.

The time until a repeat injection was administered will be analyzed using a Cox proportional hazards survival model and chi-squared tests will be used to analyze repeat injections, repeat surgeries, and side effects between groups. All statistical analyses will be completed using a two-sided level of significance of 0.05.

Inclusion Criteria

- Age greater than or equal to 18
- Ability to provide informed consent
- Capable of complying with the outcome instruments used
- Capable of attending all planned follow up visits
- Patient is deemed appropriate for intra-articular hip, glenohumeral, peri-tendinous biceps, or subdeltoid bursa corticosteroid injection by their treating physician for the treatment of a painful musculoskeletal condition

-Average pain of greater than or equal to 4/10 over the last 7 days

Exclusion Criteria

- Unclear diagnosis
- Pregnancy
- Incarcerated patients
- Prior corticosteroid injection into the anatomical structure within the past 3 months
- Prior prosthetic surgery on the joint
- Any condition that increases injection risk such as bleeding tendencies, uncontrolled diabetes, current active infection, or infection requiring antibiotics within the last 7 days
- Chronic opioid use to control pain
- Workers compensation and litigation.
- BMI > 40

Data safety monitoring

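### No outcome, visit or model contrast is designated primary and every analysis runs at 0.05; if pain is tested at each visit, the false-positive chance in a structure is about 12.5% at an assumed between-visit correlation of 0.5, against 5% for one overall contrast.

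*Combined protocol and SAP*

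**What the plan says.** The heading of section 5 asks for an explicit primary hypothesis or goal. The heading of section 8 asks for "the statistical plan for analyzing at least the primary hypothesis".

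The text beneath them gives:

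- Aim (a): which steroid type better treats pain in the hip, "glenohumeral joint, biceps tendon, and subacromial bursa at 2 weeks, 3 months, or 6 months".
- Aim (b): "To determine if there is a significantly different side effect profile between particulate and non-particulate corticosteroids".
- Hypothesis: "There will be no significant difference in pain reduction, number of injections received, conversion to surgery, or side effect profile", at the same three times.
- Section 8, Data analysis: the four structures are analysed separately. In each, a mixed-effects model compares pain, function and the number of subsequent injections. On how the model is built: "These models will include adjustments for repeated measures and potential covariates as determined by the previous univariate tests". A Cox model for time to repeat injection follows, then chi-squared tests for repeat injections, surgeries and side effects.
- Power statement, same section: "at least 80% power to detect 10% differences in pain and 25% differences in function". It names no visit and no contrast.
- Error rate: "All statistical analyses will be completed using a two-sided level of significance of 0.05".

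No sentence ranks these analyses, and no multiplicity rule is stated.

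**The concern.** Pain is the lead efficacy question because aim (a) is about nothing else. Even if it is taken as primary by implication, two things stay open. The first is the visit, because aim (a) joins the three times with 'or'. The second is the model contrast. Adjusting for repeated measures deals with the correlation between a patient's own scores. It does not say whether the reported result is one treatment effect over follow-up or an effect at each visit.

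A team following this plan to the letter could report a difference at 2 weeks alone as the answer to aim (a). It could equally report a null overall contrast. Nothing in the document would show which was planned. The trial is meant to guide the choice of steroid, so this is more than a missing detail, and it cannot be credibly repaired once results are known.

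The covariate rule adds to the problem. Covariates enter according to univariate tests on the collected data, so the pain model itself is not fixed in advance.

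**Working it through.** **The plan's own figure.** The stated sizes are 25 per group (bursa and hip), 18 (glenohumeral) and 31 (biceps). They cannot be reproduced, because no standard deviation, visit or base for the percentages is given. They therefore do not reveal which contrast the authors had in mind.

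**Inputs from the documents.** Two-sided level 0.05 for each analysis (Data analysis); k = 3 post-injection pain assessments, at 2 weeks, 3 months and 6 months (Design); four structures analysed separately.

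**Input assumed.** Between-visit correlation r of the pain scores, taken as equal for all pairs of visits. The documents give none, so r runs from 0 to 0.9.

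**One overall contrast.** One test at 0.05 gives 5%.

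**Three visit tests, r = 0.** 1 − 0.95³ = 1 − 0.8574 = 0.143.

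**Three visit tests, r > 0.** With c = 1.96, and φ and Φ the standard normal density and distribution function:

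P(at least one false positive) = 1 − ∫ φ(u) · [Φ((c − √r·u)/√(1−r)) − Φ((−c − √r·u)/√(1−r))]³ du

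| r | Chance of at least one false pain difference in a structure |
|---|---|
| 0 | 14.3% |
| 0.3 | 13.6% |
| 0.5 | 12.5% |
| 0.7 | 10.9% |
| 0.9 | 8.4% |
| 0.95 | 7.3% |

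**Checks.**

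- Simulated t-tests at 18, 25 and 31 per group gave 14.0% to 14.2% at r = 0, 12.3% to 12.8% at r = 0.5 and 8.3% to 8.6% at r = 0.9. The overall contrast gave 4.9% to 5.1%.
- With correlation that decays over time (first-order autoregressive), the figures are 12.9% at 0.5 and 8.8% at 0.9.
- If the overall average is also open to choice alongside the three visits, simulation gives 12.9% at r = 0.5 (16.1% at 0, 8.4% at 0.9).

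**Across structures, with one primary test in each.** 1 − 0.95⁴ = 1 − 0.8145 = 0.185 if the four are independent. Independence is not exact, because one patient may contribute to two structures: "Any injection into a separate space (i.e. glenohumeral joint followed by subdeltoid bursa) will be considered different structures". At an assumed correlation of 0.3 between the four tests, the figure is 17.4%.

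**The case against.** The strongest reply is that a mixed model comparing pain between groups is naturally read as having one treatment term, and then the pain error rate is 5%. A joint group-by-time test would also be a single 5% test. This stands as far as it goes, and it is why the higher figures are conditional. It does not settle the point, because the plan states neither reading and aim (a) invites a visit-by-visit answer.

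A second reply is that 14.3% needs uncorrelated scores from the same patients, which is implausible. That is fair. It is the upper end of an assumed range, and high correlation brings the figure down towards 8% or a little below.

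Third, accepting about 18.5% over four structures may look inconsistent with objecting to 12.5% within one. The distinction can be defended: the plan analyses the structures separately, so each conclusion concerns its own structure. Within a structure, several tests compete to answer one question.

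A reader might also infer that the trial is underpowered for a single visit and needs more patients. The documents do not support that. The power claim is for at least 80%, for pain and function together, so pain power may exceed 80%. As an illustration, suppose the 25 per group gave the three-visit average exactly 80% power. One visit at r = 0.5 would then have 63%. Had it been 90% or 95%, one visit would have 75% or 84%. Nothing in the documents says which applies, or that the average was assumed at all.

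**Conclusion.** The concern holds. No primary outcome, visit or contrast is named where the plan's own headings call for a primary hypothesis, and every analysis runs at 0.05 unranked. If pain is tested at each visit, the chance of a false pain difference in a structure is about 12.5% at r = 0.5 (14.3% at 0, 8.4% at 0.9), against 5% for one overall contrast. The correlation is an assumption, and the condition matters: the documents do not support saying that the trial's pain error rate is 12.5%, only that the plan permits it. The figure covers pain in one structure and leaves out function, injections, surgery and side effects.

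This must be fixed before data are seen. No shortfall in enrolment is claimed. The missing standard deviation and the undefined percentages in the power statement are a separate matter.

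**What to change.** Before data are seen, state in sections 5 and 8:

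- **Primary.** In each structure, the single primary analysis is the mixed-model treatment difference in average NRS, either averaged over the three visits or at one visit named by the sponsor, at two-sided 0.05. Baseline NRS and any other covariates are fixed in advance and not selected by the univariate baseline tests.
- **Secondary.** Other visits, function, repeat injections and surgery are reported as estimates with 95% confidence intervals.
- **Safety.** Side effects are the separate question of aim (b), reported in the same way.
- **Scope.** Conclusions are structure-specific, with about an 18.5% chance of at least one false positive over the four primary tests if they are treated as independent.

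Reword both aims, the hypothesis and the blanket 0.05 sentence to match. If the sample size was calculated for a different contrast, restate the power for the chosen one. The documents favour no visit, so that choice is the sponsor's.

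**Cost.** Wording only, with no new procedures and no added enrolment proposed. Secondary results can no longer be headlined as significant. Averaging dilutes a difference present at one visit only. The restated power may be less favourable.
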